11.1.4 Response Criteria

11.1.4.1 Evaluation of Target Lesions (Note: irradiated target lesions are excluded from overall response determination)

Complete Response (CR): Disappearance of all target lesions. Any pathological lymph nodes (whether target or non-target) must have reduction in short axis to <10 mm.

Partial Response (PR): At least a 30% decrease in the sum of the diameters of target lesions, taking as reference the baseline sum diameters.

Progressive Disease (PD): At least a 20% increase in the sum of the diameters of target lesions, taking as reference the smallest sum on study (this includes the baseline sum if that is the smallest on study). In addition to the relative increase of 20%, the sum must also demonstrate an absolute increase of at least 5 mm. (Note: the appearance of one or more new lesions is also considered progressions).

Stable Disease (SD): Neither sufficient shrinkage to qualify for PR nor sufficient increase to qualify for PD, taking as reference the smallest sum diameters while on study.

11.1.4.2 Evaluation of Non-Target Lesions

Complete Response (CR): Disappearance of all non-target lesions and normalization of tumor marker level. All lymph nodes must be non-pathological in size (<10 mm short axis).

Note: If tumor markers are initially above the upper normal limit, they must normalize for a patient to be considered in complete clinical response.

Non-CR/Non-PD: Persistence of one or more non-target lesion(s) and/or maintenance of tumor marker level above the normal limits.

Progressive Disease (PD): Appearance of one or more new lesions and/or *unequivocal progression* of existing non-target lesions. *Unequivocal progression* should not normally trump

target lesion status. It must be representative of overall disease status change, not a single lesion increase.

Although a clear progression of “non-target” lesions only is exceptional, the opinion of the treating physician should prevail in such circumstances, and the progression status should be confirmed at a later time by the review panel (or Principal Investigator).

The finding of a new lesion should be unequivocal (i.e. not due to difference in scanning technique, imaging modality, or findings thought to represent something other than tumor (for example, some ‘new’ bone lesions may be simply healing or flare of pre-existing lesions). However, a lesion identified on a follow-up scan in an anatomical location that was not scanned at baseline is considered new and will indicate PD. If a new lesion is equivocal (because of small size etc.), follow-up evaluation will clarify if it truly represents new disease and if PD is confirmed, progression should be declared using the date of the initial scan on which the lesion was discovered.

11.1.4.3 Evaluation of Best Overall Response

The best overall response is the best response recorded from the start of the treatment until disease progression/recurrence (taking as reference for progressive disease the smallest measurements recorded since the treatment started). The participant's best response assignment will depend on the achievement of both measurement and confirmation criteria.

Table 9: For Patients with Measurable Disease (i.e., Target Disease)

Target Lesions	Non-Target Lesions	New Lesions	Overall Response	Best Overall Response for when Confirmation is Required:
CR	CR	No	CR	≥4 wks confirmation
CR	Non-CR/Non-PD	No	PR	
CR	Not evaluated	No	PR	≥4 wks confirmation
PR	Non-CR/Non-PD/Not evaluated	No	PR	
SD	Non-CR/Non-PD/Not evaluated	No	SD	Documented at least once ≥4 wks from baseline
PD	Any	Yes or No	PD	No prior SD, PR or CR
Any	PD*	Yes or No	PD	
Any	Any	Yes	PD	

CONFIDENTIAL

This document is confidential. Do not disclose or use except as authorized.

* In exceptional circumstances, unequivocal progression in non-target lesions may be accepted as disease progression.

Note: Participants with a global deterioration of health status requiring discontinuation of treatment without objective evidence of disease progression at that time should be reported as "*symptomatic deterioration*". Every effort should be made to document the objective progression even after discontinuation of treatment.

Tbale 10: For Participants with Non-Measurable Disease (i.e., Non-Target Disease)

Non-Target Lesions	New Lesions	Overall Response
CR	No	CR
Non-CR/non-PD	No	Non-CR/non-PD*
Not all evaluated	No	not evaluated
Unequivocal PD	Yes or No	PD
Any	Yes	PD

* 'Non-CR/non-PD' is preferred over 'stable disease' for non-target disease since SD is increasingly used as an endpoint for assessment of efficacy in some trials so to assign this category when no lesions can be measured is not advised

11.1.5 Duration of Response

Duration of overall response: The duration of overall response is measured from the time measurement criteria are met for CR or PR (whichever is first recorded) until the first date that recurrence or PD is objectively documented, taking as reference for PD the smallest measurements recorded since the treatment started.

Duration of overall complete response: The duration of overall CR is measured from the time measurement criteria are first met for CR until the first date that recurrent disease is objectively documented.

Duration of stable disease: Stable disease is measured from the start of the treatment until the criteria for progression are met, taking as reference the smallest measurements recorded since the treatment started.

11.1.6 Clinical Benefit rate

Clinical benefit rate: defined as CR, PR and stable disease (SD) ≥ 24 weeks.

11.2 Other response parameters

11.2.1 Definition of Tumor Response Using Immune-Related Response Criteria (irRC)

CONFIDENTIAL

This document is confidential. Do not disclose or use except as authorized.

The sum of the longest diameter of lesions (SPD) at tumor assessment using the immune-related response criteria (irRC) for progressive disease incorporate the contribution of new measurable lesions. Each net Percentage Change in Tumor Burden per assessment using irRC criteria accounts for the size and growth kinetics of both old and new lesions as they appear.

11.2.2 Impact of New Lesions on irRC

New lesions in and of themselves do not qualify as progressive disease. However, their contribution to total tumor burden is included in the SPD which in turn feeds into the irRC criteria for tumor response. Therefore, new non-measurable lesions will not discontinue any subject from the study.

11.2.3 Definition of Target Lesions Response Using irRC

- **irComplete Response (irCR):** Complete disappearance of all target lesions. This category encompasses exactly the same subjects as “CR” by the mWHO criteria.
- **irPartial Response (irPR):** Decrease, relative to baseline, or 50% or greater in the sum of the products of the two largest perpendicular diameters of all target and all new measurable target lesions (i.e., Percentage Change in Tumor Burden). Note: the appearance of new measurable lesions is factored into the overall tumor burden, but does not automatically qualify as progressive disease until the SBD increases by $\geq 25\%$ when compared to SPD at nadir.
- **irStable Disease (irSD):** Does not meet criteria for irRC or irPR, in the absence of progressive disease.
- **irProgressive Disease (irPD):** At least 25% increase Percentage Change in Tumor Burden (i.e. taking SPD of all target lesions and any new lesions) when compared to SPD at nadir.

11.2.4 Definition of Non-Target Lesions Response Using irRC

- **irComplete Response (irCR):** Complete disappearance of all non-target lesions. This category encompasses exactly the same subjects as “CR” by the mWHO criteria.
- **irPartial Response (irPR) or irStable Disease (irSD):** Non-target lesion(s) are not considered in the definition of PR; these terms do not apply.
- **irProgressive Disease (irPD):** Increases in number or size of non-target lesion(s) does not constitute progressive disease unless/until the Percentage Change in Tumor Burden increases by 25% (i.e. the SPD at nadir of the target lesions increases by the required amount).

11.2.5 Definition of Overall Response Using irRC

Overall response using irRC will be based on these criteria:

- **Immune-Related Complete Response (irCR):** Complete disappearance of all tumor lesions (target and non-target) together with no new measurable/unmeasurable lesions for at least 4 weeks from the date of documentation of complete response.
- **Immune-Related Partial Response (irPR):** The sum of the products of the two largest perpendicular diameters of all target lesions is measured and captured as the SPD baseline. At each subsequent tumor assessment, the SPD of the two largest perpendicular diameters of all target

CONFIDENTIAL

This document is confidential. Do not disclose or use except as authorized.

lesions and of new measurable lesions are added together to provide the Immune Response Sum of Product Diameters (irSPD). A decrease, relative to baseline, of the irSPD compared to the previously SPD baseline of 50% or greater is considered an irPR.

- **Immune-Related Stable Disease (irSD):** irSD is defined as the failure to meet criteria for immune complete response or immune partial response, in the absence of progressive disease
- **Immune-Related Progressive Disease (irPD):** It is recommended in difficult cases to confirm PD by serial imaging. Any of the following will constitute PD:
 - At least 25% increase in the SPD of all target lesions over baseline SPD calculated for the target lesions.
 - At least 25% increase in the SPD of all target lesions and new measurable lesions (irSPD) over the baseline SPD calculated for the target lesions.

Criteria for determining overall response by irRC are summarized as follows:

Immune-Related Response Criteria Definitions

Target Lesion Definition	Non-Target Lesion Definition	New Measurable Lesions	New Unmeasurable Lesions	Percent change in tumor burden (including measurable new lesions when present)	Overall irRC Response
Complete Response	Complete Response	No	No	-100%	irCR
Partial Response	Any	Any	Any	≥ -50%	irPR
				< -50% to < +25%	irSD
				> +25%	irPD
Stable Disease	Any	Any	Any	< -50% to < +25%	irSD
				> +25%	irPD
Progressive Disease	Any	Any	Any	≥ +25%	irPD

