5.8 Criteria for Taking a Participant Off Protocol Therapy

Duration of therapy will depend on individual response, evidence of disease progression and tolerance. In the absence of treatment delays due to adverse event(s), treatment may continue until one of the following criteria applies:

- Disease progression. In the case of progressive disease, confirmatory scans are recommended between 4-8 weeks following the date of initial progression along with continued treatment, provided the patient is thought to be deriving clinical benefit and is counseled regarding the risks and benefits of continued treatment. If progression is confirmed, date of progression is dated at the time of the original scans. If progression is confirmed, continued treatment is only allowed if irRC demonstrates a response or stable disease, again provided the patient is thought to be clinically benefitting and is counseled regarding the risk and benefits of remaining on treatment.
- Intercurrent illness that prevents further administration of treatment
- Unacceptable adverse event(s)
- Participant demonstrates an inability or unwillingness to comply with the oral medication regimen and/or documentation requirements
- Participant decides to withdraw from the protocol therapy
- General or specific changes in the participant's condition render the participant unacceptable for further treatment in the judgment of the treating investigator

Participants will be removed from the protocol therapy when any of these criteria apply. The reason for removal from protocol therapy, and the date the participant was removed, must be documented in the case report form (CRF). Alternative care options will be discussed with the participant.

A Treatment Ended/Off Study Form will be filled out within OnCore, when a participant is removed from protocol therapy.

In the event of unusual or life-threatening complications, treating investigators must immediately notify the Overall PI, [name] at [name] (pager #).

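### irRC progression is measured from the nadir in 11.2.3 and 11.2.4 but from baseline in 11.2.5, so a tumor that shrinks and then regrows can get opposite answers at the section 5.8 treatment-continuation rule

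*Combined protocol and SAP*

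**What the plan says.** **Nadir as reference.** Section 11.2.3 defines target-lesion irPD as a rise of at least 25%, "taking SPD of all target lesions and any new lesions) when compared to SPD at nadir". Its note on new lesions, placed under irPR, says that their appearance "does not automatically qualify as progressive disease until the SBD increases by" at least 25%, again against the nadir. Section 11.2.4 says that non-target growth is not progression unless the tumor burden rises by 25%, and explains this as the point at which "the SPD at nadir of the target lesions increases by the required amount".

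**Baseline as reference.** Section 11.2.5 defines overall irRC response and gives two routes to irPD. The first is "At least 25% increase in the SPD of all target lesions over baseline SPD calculated for the target lesions". The second is the same percentage rise in the SPD of target lesions plus "new measurable lesions (irSPD) over the baseline SPD calculated for the target lesions".

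**Response.** The irPR threshold is anchored to baseline in both 11.2.3 and 11.2.5. In the latter: "A decrease, relative to baseline, of the irSPD compared to the previously SPD baseline of 50% or greater is considered an irPR".

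**Where the status is used.** Under section 5.8, once progression has been confirmed, "continued treatment is only allowed if irRC demonstrates a response or stable disease". Perceived clinical benefit and counselling are also required. Section 13.5 lists overall response per irRC as a secondary endpoint, and 11.2.7 applies irRC to irradiated lesions to define local response. The primary objective (1.2) uses RECIST 1.1.

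**The concern.** These are operative definitions in current text, and two readers can each follow the protocol and reach different irRC classifications of one scan. That matters most where the classification triggers an action. Section 5.8 has no irRC definition of its own and relies on section 11.2. A patient with confirmed progression may therefore be allowed to continue under one section and not under another. RECIST progression in 11.1.4.1 is itself measured from the smallest sum on study, so patients who shrink and then regrow can reach this decision, and they are the patients on whom the two irRC references can differ.

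**Working it through.** The plan states no figure to reproduce. The check applies both rules to the same scan. The tumor sizes are illustrative assumptions; the thresholds are the protocol's.

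**Rules.** Let B be baseline SPD, N the nadir and S the current SPD including new measurable lesions.
- Nadir rule (11.2.3, 11.2.4): irPD if S/N − 1 ≥ 25%.
- Baseline rule (11.2.5): irPD if S/B − 1 ≥ 25%; irPR if S/B − 1 ≤ −50%; otherwise irSD (setting aside complete response).

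**Where they disagree.** 1.25 × N ≤ S < 1.25 × B. This range exists only if N < B. With B = 100 and N = 60, it runs from 1.25 × 60 = 75 to just under 1.25 × 100 = 125.

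**Cases, with B = 1000.**

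| Nadir | Current | Change from nadir | Nadir rule | Change from baseline | Baseline rule |
|---|---|---|---|---|---|
| 1000 | 1250 | +25.0% | irPD | +25.0% | irPD |
| 900 | 1130 | +25.6% | irPD | +13.0% | irSD |
| 800 | 1000 | +25.0% | irPD | 0.0% | irSD |
| 600 | 800 | +33.3% | irPD | −20.0% | irSD |
| 300 | 450 | +50.0% | irPD | −55.0% | irPR |

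The last row needs S ≤ 0.5 × B as well as S ≥ 1.25 × N, so it requires a nadir at or below 0.5/1.25 = 40% of baseline.

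**How far apart the thresholds are.** The regrowth from nadir that the baseline rule requires is 1.25/(N/B) − 1. For N/B of 0.9, 0.8, 0.6 and 0.5 this is 39%, 56%, 108% and 150%, against 25% under the nadir rule.

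**At the section 5.8 decision.** Take one non-irradiated, non-nodal target lesion: 40 × 25 mm at baseline, 30 × 20 mm at nadir, 37 × 24 mm now.
- RECIST: the longest diameter goes from 30 to 37 mm, which is +23.3% and +7 mm. This meets the 20% and 5 mm conditions for progression.
- SPD: 1000, then 600, then 37 × 24 = 888.
- From nadir: 888/600 − 1 = +48.0%, irPD, so the irRC condition in 5.8 is not met.
- From baseline: 888/1000 − 1 = −11.2%, irSD, so the irRC condition is met.

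**How little shrinkage is needed.** Assume equal growth in both axes, non-nodal lesions and no new lesions. The RECIST threshold of +20% in diameter is then 1.2² = 1.44, or +44% in products, which is irPD from nadir. From baseline, a scan at that threshold is not irPD if N/B < 1.25/1.44 = 0.87. Since √0.87 ≈ 0.93, that is about 7% linear shrinkage.

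**Whether the table settles it.** Its percent-change column names no reference. The tumor-burden term does not supply one either: 11.2.3 uses it with baseline for irPR and with the nadir for irPD. If the column is read from baseline, target-lesion progression from nadir that is less than 25% above baseline has no row.

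**The case against.** One defence is that 11.2.3 describes target lesions and 11.2.5 overall response, so each may have its own reference. This does not hold. Both sections apply the 25% rule to target plus new-lesion SPD, and the 11.2.5 table carries target-lesion progression into overall irPD.

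The stronger objections concern consequence, and they stand:
- A reader might infer that any shrinkage produces conflicting classifications. It does not: with baseline 100, nadir 60 and current SPD 65, neither rule gives irPD. Regrowth into the disputed range is required, and if the nadir equals baseline the rules always agree.
- A reader might infer that irRC response rates are unreliable. irPR is measured from baseline in both sections, and irBOR in 11.2.6 is the best confirmed response using all assessments, so later irPD does not by its terms cut it off. What remains is narrow: a confirmatory scan at least 50% below baseline yet at least 25% above nadir.
- The primary objective uses RECIST 1.1, so the 3-month classification is not directly changed.
- Shrinkage expected in irradiated lesions is a weak argument for the 5.8 effect. Those lesions are scored separately as local response, RECIST overall response excludes irradiated target lesions (11.1.4.1), and the documents do not say whether overall irRC includes them.
- The 5.8 rule applies only after confirmed progression, alongside other conditions, in a trial of at most 26 patients (13.2).

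The other wording problems are editorial. Section 11.2.1 describes SPD as "The sum of the longest diameter of lesions (SPD) at tumor assessment", but 11.2.3 and 11.2.5 spell out products of perpendicular diameters. The table's irPR and irSD bounds are loose in sign, but the prose beside them is clear.

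**Conclusion.** The point holds in a limited form. The nadir and baseline definitions conflict, and no passage ranks them. For a tumor that falls below baseline and regrows to between 1.25 × nadir and 1.25 × baseline, the same scan is irPD under 11.2.3 but irSD under 11.2.5, or irPR if it is still at least 50% below baseline. The consequence that matters is the section 5.8 continuation decision, where the two readings can give opposite answers. Effects on irRC response rates are small, and there is no direct effect on the primary endpoint.

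The size of the disputed range is exact arithmetic on assumed tumor sizes. The number of patients affected cannot be derived, because the documents do not say how many would shrink and then regrow.

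A reader might also infer that the nadir must be the intended reference because it appears more often. The documents do not support that: one instance is a note under irPR, the wording in 11.2.4 is unclear, and 11.2.5 is the section that defines overall response.

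**What to change.** The sponsor should reconcile 11.2.3, 11.2.4, both irPD bullets in 11.2.5 and the 11.2.5 table to one stated reference SPD, naming it in the table's percent-change column. The protocol should also state which irRC definition section 5.8 uses. Choosing the reference in effect sets who may continue treatment, so that choice belongs to the sponsor and investigators and none is proposed here.

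As minor clean-up, define SPD in 11.2.1 as the sum of products of perpendicular diameters, as 11.2.3 and 11.2.5 already do. Write the table's irPR and irSD bounds to match the prose: irPR is a decrease of 50% or more, and irSD begins at a smaller decrease.

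The cost is protocol wording, and possibly re-reading irRC status from existing scans for patients already assessed. No new scans are needed.

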11.2.6 Immune-Related Best Overall Response Using irRC (irBOR)

irBOR is the best confirmed overall response over the study as a whole, recorded between the date of first dose until the last tumor assessment before subsequent therapy (except for local palliative radiotherapy for painful bone lesions) for the individual subject in the study. For the assessment of irBOR, all available assessments per subject are considered.

irCR or irPR determinations included in the irBOR assessment must be confirmed by a second (confirmatory) evaluation meeting the criteria for response and performed no less than 4 weeks after the criteria for response are first met.

11.2.7 Local response is defined as irRC applied to the irradiated lesions. This is not applicable in the case of an irradiated bone lesion.

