Following this first cycle, pembrolizumab will be continued every 3 weeks. Radiation will, in general, not be repeated during subsequent cycles, except as at the discretion of the Principal Investigator in the case of patients thought to be deriving overall benefit from treatment.

Cohort B: Pembrolizumab and hypofractionated and low dose radiation to multiple lesions

In contrast to Cohort A where a single lesion is irradiated, the goal of cohort B is to irradiate a significant, if not total, volume of visible disease in order to predispose for a systemic immune response. Pembrolizumab will be given within 10 days after starting radiotherapy treatment, or up to 3 days prior to radiotherapy start. Patients in cohort B will receive hypofractionated palliative radiation starting on day 1 to a dose of 8 Gy in each of 3-5 fractions no more frequently than every other day to 1-3 lesions. If the treating radiation believes a dose of 8 Gy is not indicated due to the clinical situation, the dose of radiation may be reduced to 5-6 Gy per fraction. In patients where there are other potential lesions to irradiate, these subjects may also receive palliative radiation to a dose of 20 Gy in 5 fractions to an additional 1-3 lesions, with the goal of treating a significant burden of the patient's measurable disease. Radiation should be completed over a period of approximately 14-21 calendar days, or if more than 3 lesions are irradiated may be partially delivered during the second cycle given logistical radiation planning and treatment constraints. 8

CONFIDENTIAL

This document is confidential. Do not disclose or use except as authorized.

Gy radiation doses will not be given on consecutive days; however, low dose radiation may be administered on subsequent days or on the same days as high dose radiation is administered. In general, a maximum of 2-3 lesions will be treated on any single day, although treating up to 4 lesions is allowed.

Following this first cycle, pembrolizumab will be continued every 3 weeks. Radiation may be administered during subsequent cycles to other lesions using either 5-8 Gy in each of 3-5 fractions or 20 Gy in 5 fractions as deemed appropriate.

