MD/NP/PA evaluation required		X		X		X	X	
Survival								X ^m
HIV Test ⁿ	X							

CONFIDENTIAL

This document is confidential. Do not disclose or use except as authorized.

^a Baseline evaluations are to be conducted within 28 days prior to start of protocol therapy. If these screening assessments occur within 3 days before start of study treatment, then they may serve as the baseline Cycle 1 Day 1 values. Baseline Laboratory tests must be completed within 14 days prior to first dose of the study drug.

^b As described in section 5, pembrolizumab may start up to 3 days before and 10 days after radiotherapy start, although it is encouraged that pembrolizumab be started after at least several fractions of radiation have been administered. Radiation will be delivered as specified as per Cohort A (5-8 Gy in each of 3-5 fractions) or Cohort B (8 Gy in each of 3-5 fractions to 1-3 lesion, and 20 Gy in 5 fractions to 1-3 additional lesions). As specified in the protocol, radiotherapy during subsequent cycles is acceptable with permission of the PI.

^c See Section 5 for concomitant medications guidelines

^d Chloride, potassium, sodium, BUN, serum creatinine, phosphorus, calcium, albumin, total protein, alkaline phosphatase, ALT, AST, total bilirubin (NOTE: the frequency of checking magnesium levels is left up to the treating provider)

^e In female subjects with child-bearing potential, urine pregnancy test must be performed within **7 days** before the first dose of study medication. If the urine test is positive or cannot be confirmed as negative, then a serum test is required to confirm the subject is not pregnant.

^f Archival tumor samples should be collected (block or if not possible, 20 unstained slides) – both the most recent biopsy as well as prior to the start of any PD-1 directed therapy.

^g Baseline tumor biopsy obtained within 28 days before starting protocol therapy is suggested for those with accessible tumor tissue. See Section 9.1.2 for biopsy handling and processing instructions.

^h A second optional tumor biopsy will be performed in patients at the end of cycle 2, prior to cycle 3 day 1 of protocol therapy (ideally as close to administration of cycle 3 day 1 therapy as possible).

ⁱ For those taken off the study for toxicity tumor measurements should be repeated every 6 weeks. Patients with documented PD will be removed from the treatment and followed for overall survival every 6 months, until death (by phone).

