11.2.8 Abscopal response rate

Abscopal response is defined as described previously [62] to be a decrease in the longest diameter of at least 30% in any measurable (>1cm) non-irradiated lesion from baseline. A complete abscopal response is defined as the complete disappearance of a measurable non-irradiated lesion and a partial abscopal response was defined as at least a 3-% decrease in the longest diameter. Progressive disease in this context is defined as at least a 20% increase in the longest diameter of the best measurable non-irradiated lesion, whereas stable disease was defined as insufficient shrinkage or growth to qualify for a partial abscopal response or complete abscopal response or progressive disease.

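### Lesions first irradiated in cycle 2 or later have no reference scan of their own, so earlier growth can hide an in-field response, and abscopal status is undated.

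*Combined protocol and SAP*

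**What the plan says.** Section 1.3 makes local response rates in the irradiated fields, and abscopal response rates, secondary objectives. Section 13.5 reports response rates descriptively, with 90% exact binomial intervals and no test.

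For local response, Section 11.2.7 says: "Local response is defined as irRC applied to the irradiated lesions". It excludes irradiated bone lesions and names no reference scan of its own.

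The irRC reference is in Section 11.2.5. The SPD of the target lesions is "captured as the SPD baseline", and the response rule reads: "A decrease, relative to baseline, of the irSPD compared to the previously SPD baseline of 50% or greater is considered an irPR". Progression in the same section is "At least 25% increase in the SPD of all target lesions over baseline SPD calculated for the target lesions". Section 11.1.3 places baseline before treatment, at most 4 weeks earlier. Section 10 accepts a newer measurement from the radiation simulation scan, but only before study treatment starts.

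On later radiation, Section 5.1 says for cohort B: "Radiation may be administered during subsequent cycles to other lesions". It also lets part of the first course run into cycle 2 when more than three lesions are treated. Cohort A is tighter: "Radiation will, in general, not be repeated during subsequent cycles, except as at the discretion of the Principal Investigator". A footnote to the study calendar adds that "radiotherapy during subsequent cycles is acceptable with permission of the PI".

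Section 11.2.8 defines abscopal response as "a decrease in the longest diameter of at least 30% in any measurable (>1cm) non-irradiated lesion from baseline".

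**The concern.** The objective is response within a radiation field. For a lesion first treated in cycle 2 or later, a change measured from study baseline combines two periods: one before its field existed, and one after. Growth in the first period offsets shrinkage in the second, so the figure no longer describes what followed radiation to that lesion.

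This does not need a very late event. The first on-study scan is at week 5, plus or minus one week (Section 5.3.1). That spans days 22 to 42, which is cycle 2 of a 21-day schedule. A lesion deferred into cycle 2 can be scanned and scored before its own first fraction.

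The abscopal definition has a related gap. Whether a lesion counts as non-irradiated changes when it is treated, and the definition does not say at what date this is judged. Section 9.3.3 correlates lesion rankings with abscopal responses, so the ambiguity carries into that analysis too.

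**Working it through.** The plan gives no figure for local response, so there is none to reproduce. The check applies the plan's own cut-offs.

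**Inputs.** From Section 11.2.5: irPR at a 50% or greater fall from baseline SPD, and irPD at a 25% or greater rise over it. Assumed, because the documents do not give them: g, the fractional SPD growth from study baseline to the lesion's first fraction (0 to 150%), and s, the fractional SPD shrinkage after it (30 to 80%).

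**Formulas.** Set baseline SPD to 1. The lesion measures 1+g just before its radiation and (1+g)(1-s) afterwards.

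- Change from the pre-radiation scan: -s. irPR needs s of at least 50%, whatever g is.
- Change from study baseline: (1+g)(1-s) - 1. irPR needs s of at least 1 - 0.5/(1+g).
- After radiation the lesion still reads irPD against baseline only if s is at most 1 - 1.25/(1+g).

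| g | Shrinkage needed for irPR against study baseline | Still irPD after radiation if shrinkage is at most |
|---|---|---|
| 0% | 50.0% | never |
| 10% | 54.5% | never |
| 20% | 58.3% | never |
| 25% | 60.0% | 0% |
| 50% | 66.7% | 16.7% |
| 100% | 75.0% | 37.5% |
| 150% | 80.0% | 50.0% |

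**Single-lesion illustrations.**

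- g = 20%, s = 55%: 1.20 × 0.45 = 0.54, so -46% from baseline (irSD) against -55% from the pre-radiation scan (irPR). The earlier growth is √1.20 - 1 = 9.5% per diameter.
- g = 40%, s = 60%: 1.40 × 0.40 = 0.56, so -44% (irSD) against -60% (irPR).
- 20×20 mm at baseline (400), 26×26 mm at first irradiation (676), 18×18 mm after (324): 324/400 - 1 = -19% (irSD) against 324/676 - 1 = -52% (irPR). Before radiation it already reads 676/400 - 1 = +69% (irPD).
- g = 50%, s = 70%: 1.50 × 0.30 = 0.45, so -55%. This is irPR on either reference; large shrinkage survives the earlier growth.

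The usual error is therefore irPR recorded as irSD. The 4-week confirmation rule in Section 11.2.6 applies on either reference and does not remove the contrast. The direction depends on the sign of g: a lesion that first shrank by 20% would need only 1 - 0.5/0.80 = 37.5% further shrinkage.

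**Abscopal rule.** Take a lesion of 20 mm at baseline and 13 mm on a scan before its own radiation: 13/20 - 1 = -35%, an abscopal response. If status is judged at the end of follow-up, that response is lost once the lesion is treated. If status is judged at baseline, a lesion that stays at 20 mm, is then irradiated and falls to 13 mm counts as abscopal because of its own radiation. Only judging status at the scan date avoids both errors, and the section does not say so.

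**The case against.** The strongest reply is that the plan is silent rather than wrong. Section 11.2.7 never says that later-irradiated lesions enter the local rate, or that study baseline is their reference. That is fair: both follow by default from applying irRC to the irradiated lesions. But no other rule is offered, so an analyst following the text would arrive there.

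A reader might infer that growth before radiation counts as local failure. The documents do not support that. They define no local failure endpoint. In a response rate irSD and irPD are equally non-responses, and Section 11.2.6 keeps the best confirmed response, so an early irPD does not cancel a later confirmed irPR. What remains is a missed response.

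A reader might also say that each affected lesion moves the rate by 1/19 = 5.3 points. That mixes units. Nineteen is the patient number for the 3-month PFS decision, not a stated denominator for local response. Since irRC sums lesions, a later-treated lesion would usually be one term beside those of the initial course, which dilutes its effect at patient level.

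It can be objected that a lesion growing from 20 to 26 mm (+30%, +6 mm) might itself mean RECIST progression and, under Section 5.8, end treatment before later radiation. That limits the large-growth examples. It does not reach the g = 20% case, which lies below both the 20% diameter and the 25% SPD thresholds.

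Nor do the documents show that later-treated lesions are the ones that grew. Section 5.1 attributes running into cycle 2 to logistics. Selection of grown lesions is plausible but is an inference. Likewise, loss of an abscopal response is only one reading of Section 11.2.8.

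**Conclusion.** The point stands as a flaw in how two secondary endpoints are defined. Cohort B permits first irradiation of lesions in cycle 2 or later, irRC response is referenced to pre-treatment baseline, and no text gives those lesions a new reference or excludes them. Under that literal reading, the shrinkage needed for irPR rises with earlier growth as tabulated, and a true in-field response can be recorded as irSD. In the abscopal rule, the undated status allows error in either direction.

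The net bias in the reported rates cannot be computed, because the documents give neither the number of such lesions nor their growth. The scope is narrow: descriptive endpoints, mainly cohort B and non-bone lesions. The local-response definition does not enter the 3-month PFS test. The change is still worth making because the better rule is clear and cheap.

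**What to change.** In Section 11.2.7, make lesions irradiated in the initial course the main local-response analysis. Classify by date of first fraction, so that a lesion deferred into cycle 2 falls in the later group. Report later-irradiated lesions separately and per lesion, using as reference the last available measurement (scheduled scan or radiation simulation scan) before that lesion's first fraction, and only scans after it. This also gives a reference to a lesion that appears after baseline and is then irradiated. In Section 11.2.8, let a lesion count for abscopal response only on scans before its own first fraction.

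While editing, settle whether irPD is measured from nadir (Section 11.2.3) or from baseline (Section 11.2.5).

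The cost is a few sentences and no change to treatment, visits or sample size. There are two small drawbacks. After week 5 scans are 8 weeks apart, so the reference may be up to about 8 weeks old where no simulation measurement is usable. And the later-irradiated lesions need a per-lesion reference in place of one summed baseline, which is why they should be reported apart.
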